This visit will begin by reviewing the subject's interim medical history, including medication history to ensure that he/she did not use any topical AD treatments on their arms or antihistamines within 7 days or oral AD treatments within 28 days of this visit. For all subjects, a focused physical exam will then be performed of the subject's bilateral arms to ensure that there is no evidence of cracks, breaks or infections of the skin on the arms. Vital signs will be taken. The localized SCORAD, modified EASI, global EASI and SCORAD grading scale will be used to rate the severity of the lesional AD skin on the subject's bilateral arms, and the extent of lesional AD skin on each arm will be recorded. Digital photographs of the lesional skin on both arms will be taken. Each photograph will also include a ruler so the scale of the lesions can be determined, as well as a card with the subject's identification number, visit date, and photograph location so that the photographs can be

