13.4.4 Analyses of Secondary and Other Endpoint(s)/Outcome(s)

Secondary Endpoints, Lesional AD skin:

1. The abundance of the AMT bacterial strains on lesional skin at baseline and after 1 week BID application of AMT.
 - a. The abundance of live *CoNS* species on lesional skin will be compared from baseline (day 28) to Day 35 after 1 week BID application of AMT cream versus placebo. This will be calculated using a two-tailed t-test for independent samples with type II error rate of 0.2 and type I error rate of 0.05.
2. The quantity of transplanted bacteria on lesional skin after stopping AMT cream 1 day, 2 days, and 4 days after last application.
 - a. Live antimicrobial *Staph* species will be measured on lesional skin at baseline (day 28), Day 35 (after 7 days of cream application), Day 36, Day 37, and Day 39 in order to evaluate the abundance of the antimicrobial *CoNS* species that remains after

stopping cream application. In order to take into account the variance of the abundance of antimicrobial *CoNS* species found on each subject's skin at baseline, we will perform CFU counts at each time point (Day 28, 35, 36, 37, and 38) and evaluate the percentage of antimicrobial species present at each time point. The percentage of antimicrobial species present at each time point will be compared between the AMT cream arm and placebo arm using a two-tailed t-test for independent samples with type II error rate of 0.2 and type I error rate of 0.05.

3. The change in abundance of *Staph aureus* on lesional skin from baseline to 1 day, 2 days, and 4 days after stopping AMT.
 - a. The abundance of live *Staph aureus* on lesional skin will be evaluated using CFU counting at baseline, 1 hour, and 4 hours after initial application of AMT or placebo cream, and after 4 and 7 days of cream application. At each time point, we will compare the AMT cream and placebo arms by using a two-tailed t-test for independent samples with a type I error rate of 0.05 and type II error rate of 0.2.
4. Change in clinical assessments, including SCORAD, modified EASI, and EASI after 1 week BID application of AMT.
 - a. A modified EASI, global SCORAD and EASI score will be assessed at baseline 1 week BID application of AMT cream or vehicle cream. Using percentage of improvement of these scores, we will compare percent reduction of AD severity between AMT cream and placebo cream using a two-tailed t-test with type I error rate of 0.05.

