13.7 Sample Size Considerations

Number of *S. aureus* colonies will be a continuous variable, and change in *S. aureus* abundance will be measured as the absolute difference in number of colony-forming units at specified time points.

The sample size was calculated using G-Power Data Analysis software for a two-tailed t-test for independent samples, type II error rate of 0.2, and type I error rate of 0.05. The values used in the analysis were determined from our pilot study in which we quantified the reduction in *S. aureus* on the forearms of 5 atopic dermatitis patients twenty-four hours after treatment with a live microbiome transplant. Since the sample size was small in this study, we used the median and median average deviation as measures of central tendency. The median *S. aureus* present on the forearms of atopic dermatitis patients at baseline was 192.86 CFU/cm² with deviation of 191.86. We observed that a log-base 10 reduction by 1 of the number of bacteria present on the forearms to be a clinically significant reduction at 24 hours, with deviation of 21.42. Using $\mu_1 = 192.86$, $\mu_2 = 19.186$, and $\sigma_1 = 191.86$, and $\sigma_2 = 21.42$, the total sample size necessary to see this difference would be $n=24$ for an unequal allocation of subjects 2:1 in the treatment to placebo groups.

Assuming a drop-out rate of 20%, we propose a total $n=27$, with $n= 18$ in the treatment group and $n= 9$ in the placebo group. Assignment to treatment or placebo groups will be determined using simple randomization with an online random number generator.

This sample size is reasonable and practical within the scope of this funding mechanism and recruitment capabilities.

An intention-to-treat analysis will be conducted that includes all subjects who had at least one follow-up visit after intervention. A per-protocol analysis will also be conducted that includes all subjects who were compliant with the full intervention regimen with no major protocol violations.

14. Identification and Access to Source Data

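### Clinical scores are tested as percent improvement with no baseline adjustment; a prespecified log-scale ANCOVA is a cheap change that may gain power

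*Combined protocol and SAP*

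**What the plan says.** Section 13.4.4, lesional item 4a, covers modified EASI, global SCORAD and EASI after one week of twice-daily application. The effect measure is a percentage: "Using percentage of improvement of these scores". The sentence continues: "we will compare percent reduction of AD severity between AMT cream and placebo cream using a two-tailed t-test". The error rate is set in the same place: "using a two-tailed t-test with type I error rate of 0.05". Items 1 to 3 of the same list also quote a type II error rate; item 4a does not. No analysis in section 13.4 includes a baseline covariate.

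The baseline data exist. At the Day 0 treatment visit (section 8.3, Visit 3) the scales "will be used to rate the severity of the lesional AD skin on the subject's bilateral arms", and the scores are repeated at Visit 5 (Day 7). Section 13.4.2 gives 18 subjects on AMT cream and 9 on placebo. Sections 3.2 and 13.7 describe simple randomisation with no stratification by severity.

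**The concern.** Percent change divides each subject's follow-up score by that subject's own baseline. This removes the influence of baseline only if follow-up is proportional to it. If the scores partly regress towards a common level, subjects who start low tend to show little improvement or apparent worsening, and subjects who start high tend to improve, whatever cream they use. A chance difference in severity between the arms then carries into the comparison, and the extra scatter costs power. With only 9 controls and no stratification, some imbalance is likely.

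What is at stake is the precision of the trial's only between-arm test of clinical severity. The validity of that test is not in question.

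**Working it through.** **1. The plan's own sample size.** Section 13.7 uses a "two-tailed t-test for independent samples, type II error rate of 0.2, and type I error rate of 0.05", with means 192.86 and 19.186 CFU/cm² and deviations 191.86 and 21.42.
- Difference: 192.86 - 19.186 = 173.674.
- SD: sqrt((191.86² + 21.42²)/2) = 136.51.
- Standardised difference: 173.674/136.51 = 1.272.
- At 2:1 this needs 16 + 8 = 24 subjects (power 80.2%), which matches the stated 24.

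The figure concerns *S. aureus* counts only. For any outcome, an unadjusted t-test at 18:9 reaches 80% power only for a standardised difference of 1.19.

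**2. Chance imbalance at 18:9.** The SD of the baseline difference between arms, in baseline SDs, is sqrt(1/18 + 1/9) = 0.41. The probability of a gap above 0.5 SD in either direction is 2 × [1 - Φ(0.5/0.408)], about 22%.

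**3. When percent change removes baseline.** Let B be the baseline score and Y the Day 7 score.
- If Y = B × R with R independent of B, then 1 - Y/B = 1 - R, and baseline drops out.
- Otherwise, suppose log B and log Y have equal variance s² and correlation ρ. The log ratio log(Y/B) has within-arm variance 2(1 - ρ)s². ANCOVA on the log scale has residual variance (1 - ρ²)s². The second divided by the first is (1 + ρ)/2, which is 0.65, 0.75, 0.85, 0.90 and 0.95 at ρ = 0.3, 0.5, 0.7, 0.8 and 0.9.

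The gain from adjustment is therefore real at low ρ and fades as ρ rises.

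**4. Simulated power, 18:9, two-sided 5%.** The documents give no CV, ρ or effect for SCORAD or EASI, so every input here is an assumption. For lognormal scores and a true 30% reduction (20,000 runs per row; 6,000 for the last):

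| CV | ρ | Percent-change t-test | Raw ANCOVA | Log ANCOVA | Log minus percent |
|---|---|---|---|---|---|
| 0.3 | 0.3 | 68% | 83% | 83% | +15 |
| 0.3 | 0.5 | 82% | 89% | 89% | +7 |
| 0.5 | 0.5 | 43% | 50% | 52% | +9 |
| 0.5 | 0.7 | 63% | 64% | 67% | +4 |
| 0.3 | 0.7 | 96.3% | 97.1% | 97.6% | +1.3 (near ceiling) |

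Extending CV to 0.7 gives a gain of about 5 to 9 points at ρ 0.5 and 2 to 4 at ρ 0.7. With smaller effects, chosen to avoid ceiling power (percent change / raw ANCOVA / log ANCOVA):
- ρ 0.8: 71/71/72% at CV 0.3 and 37/35/37% at CV 0.5.
- ρ 0.9: 75/72/74% at CV 0.3 and 37/33/36% at CV 0.5.

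Type I error was about 5% for all three methods.

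Fixing the effect at 1.2 residual SDs instead shows the same pattern with somewhat larger gains. Log ANCOVA holds about 79% power throughout. Percent change has 60 to 63% at ρ 0.3, 67 to 69% at 0.5, 74 to 75% at 0.7, 76 to 77% at 0.8 and 79 to 80% at 0.9.

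**5. Where adjustment does not help.**
- If Y = B × R with R independent of B, percent change has about 80 to 81% power and raw-scale ANCOVA 65 to 77%. Log ANCOVA trails percent change by 0 to 3 points if R is lognormal. It can trail by about 20 if R is normal with wide spread and values near zero.
- In the lognormal model with the 1.2-SD effect at ρ 0.9 and CV 0.7, raw-scale ANCOVA has 68.4% against 79.0% for percent change, a loss of 10.6 points.

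**The case against.** The strongest reply is that the planned test is valid at the 5% level, and that percent change is close to the right scale if the treatment effect is proportional to baseline. The same subject is rescored after only seven days, so a correlation of 0.8 or 0.9 is plausible, and there the gain is nil. All of this stands. Against a very high correlation, topical treatment of the arms must stop a week before Day 0, and section 12.2 accepts that withdrawal may cause flaring. Scores may still be moving at baseline. The documents do not settle the matter.

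It is also fair that this is one of twelve secondary endpoints in a phase 1 trial, that item 4a claims no power, and that the sample size rests on bacterial counts alone. No stated claim is broken.

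Two stronger readings are tempting:
- A reader might infer that the plan wastes power as a matter of fact. The documents contain nothing from which a loss could be calculated, and its sign depends on ρ and on the scale of the effect.
- A reader might infer that the result will be dominated by mild subjects. Eligibility sets no minimum SCORAD or EASI, so low denominators are possible. However, lesional skin in both antecubital fossae is required, so a zero baseline should not occur, and no score distribution is given to show such dominance.

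**Conclusion.** The point holds as a conditional one. Item 4a leaves an available baseline covariate unused in a 27-subject trial with simple randomisation, and this can lose power. For lognormal scores with CV 0.3 to 0.7, moving to log-scale ANCOVA is worth up to about 15 points at ρ 0.3, 5 to 9 at ρ 0.5, 2 to 4 at ρ 0.7 and about nothing at ρ 0.8 to 0.9. It costs 0 to 3 points under strict proportionality with a lognormal ratio, and more if the follow-up ratios spread close to zero. These figures rest on assumed distributions and effects, none of which comes from the documents.

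A reader might also infer that any ANCOVA would do. It would not: on the raw scale it can lose power, by about 10 points at high ρ and by up to about 16 under proportionality. The scale should therefore be fixed in advance and not chosen after looking at skewness. This is a worthwhile low-cost improvement to a secondary analysis; the planned analysis is not an error.

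**What to change.** Replace item 4a with a prespecified ANCOVA for each score: log Day 7 (Visit 5) score on arm, with the log Day 0 (Visit 3) score as covariate, two-sided 5%.
- State a rule for zero scores before unblinding, such as a fixed constant added to every score.
- Back-transform the arm coefficient τ to a ratio, exp(τ), and report it as a percent difference, 100 × (exp(τ) - 1), with its confidence interval.
- Keep percent change by arm as a descriptive summary.
- Name the visits. Scores are also taken at screening, and section 13.4 labels baseline and end of treatment as days 28 and 35, where section 8.3 uses Days 0 and 7.

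The cost is a short paragraph in section 13.4.4 and no new data. The downsides are the need for the zero-score rule and the possible power loss if effects are strictly proportional to baseline.

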13.4.5 Analyses of Exploratory Endpoint(s)/Outcome(s)

13.4.6 Descriptive Analyses

Background and baseline demographic, physical examination, and subject disposition data will be tabulated and presented for all enrolled subjects by randomized treatment group. Disposition will be tabulated according to the number and percentage of subjects who have: signed informed consent, provided baseline/screening information, were randomized to receive AMT cream or placebo, and completed at least one follow-up visit after intervention. Continuous data (e.g., age, body weight, height) will be summarized descriptively by mean, standard deviation, median, and range. Categorical data (e.g., gender, race, severity of disease) will be presented as enumerations and percentages. An intention-to-treat analysis will be conducted that includes all subjects who had at least one follow-up visit after intervention. A per-protocol analysis will also be conducted that includes all subjects who were compliant with the full intervention regimen with no major protocol violations.

13.5 Interim Analyses

Interim analyses will include distributions of AEs by subject population. No efficacy analyses will be performed unless specifically requested by the SO. Additional analyses may be requested by the NIAMS SO.

13.7 Sample Size Considerations

Number of *S. aureus* colonies will be a continuous variable, and change in *S. aureus* abundance will be measured as the absolute difference in number of colony-forming units at specified time points.

The sample size was calculated using G-Power Data Analysis software for a two-tailed t-test for independent samples, type II error rate of 0.2, and type I error rate of 0.05. The values used in the analysis were determined from our pilot study in which we quantified the reduction in *S. aureus* on the forearms of 5 atopic dermatitis patients twenty-four hours after treatment with a live microbiome transplant. Since the sample size was small in this study, we used the median and median average deviation as measures of central tendency. The median *S. aureus* present on the forearms of atopic dermatitis patients at baseline was 192.86 CFU/cm² with deviation of 191.86. We observed that a log-base 10 reduction by 1 of the number of bacteria present on the forearms to be a clinically significant reduction at 24 hours, with deviation of 21.42. Using $\mu_1 = 192.86$, $\mu_2 = 19.186$, and $\sigma_1 = 191.86$, and $\sigma_2 = 21.42$, the total sample size necessary to see this difference would be $n=24$ for an unequal allocation of subjects 2:1 in the treatment to placebo groups.

Assuming a drop-out rate of 20%, we propose a total $n=27$, with $n= 18$ in the treatment group and $n= 9$ in the placebo group. Assignment to treatment or placebo groups will be determined using simple randomization with an online random number generator.

This sample size is reasonable and practical within the scope of this funding mechanism and recruitment capabilities.

An intention-to-treat analysis will be conducted that includes all subjects who had at least one follow-up visit after intervention. A per-protocol analysis will also be conducted that includes all subjects who were compliant with the full intervention regimen with no major protocol violations.

14. Identification and Access to Source Data

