Figure 4 panel (a) demonstrates the effect of transplantation of antimicrobial CoNS strain(s) on survival of *S. aureus* on the skin surface of subjects with AD. *S. aureus* survival was measured on the lesional sites in both antecubital fossa of the AD subject before and 24 hours after either treatment with antimicrobial CoNS strain(s) autologously screened from the same subject or vehicle. Panel (b) illustrates *S. aureus* survival on the forearm 24 hours after treatment with autologous strain(s) of CoNS or treatment with vehicle. Relative CFU of *S. aureus* is shown as percent of baseline and different color symbols indicates data from each individual subject. In panel (c) CFUs of CoNS on the skin surface of subjects with AD were simultaneously counted as shown in panel (a). Panel (d) shows CoNS survival on the forearm 24 hours after treatment with autologous strain(s) of CoNS or treatment with vehicle. Relative CFU of CoNS is shown as percent of baseline.

In our pilot study of 5 subjects evaluating an AMT cream (IND#15786), we noted no serious adverse events (SAEs). Two subjects noted mild worsening of AD, which were deemed unrelated to the AMT cream given AMT cream was not applied on the area with worsening AD. One subject noted mild worsening of AD with an increase in pruritus and erythema on both arms. Since AMT was applied to only one arm, it is less likely that

the adverse event (AE) was related to the AMT cream given the bilateral worsening of AD on the upper extremities. Overall, the AMT cream was very well tolerated and had no significant adverse events.

2. Study Hypotheses/Objectives

Our preliminary data strongly suggest that some strains of resident CoNS act to defend the skin surface against colonization by SA. The goal of this proposal is to restore this function of the microbiome on atopic skin by replacing these beneficial bacteria. Our approach will be very safe since we will select the beneficial microbes that are normal residents of healthy skin. These bacteria will be harvested from the subject, expanded and reapplied to the same subject. An FDA IND has been approved and institutional IRB obtained for this approach (IND #15786). After application of the bacteria the survival of SA will be measured. Thus, this autologous microbiome transplant (AMT) is a first step before a generalized “probiotic” therapeutic approach.

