9.1 Skin swabs Samples

9.1.1. Skin Swab collection

The antecubital fossae bilaterally will be defined as the lesional swab location. The non-lesional swab location will be defined as the upper inner arm without AD skin. The designated site for swabbing will be marked with a pen and non-identifying digital photographs will be taken of the swabbing site for future visits. The designated site for swabbing will be measured for each subject, and the total area (cm x cm) recorded. Using a skin swab, the lateral edge of the swab will be rubbed across the measured area in a cross-wise manner while rotating the swab handle between the thumb and forefinger. Swabbing will be performed for at least 30 seconds. Up to 6 swabs may be obtained from each site.

9.1.2. *Staphylococcus aureus* Screening assay

Skin swabs will be collected from pre-measured areas of lesional and non-lesional skin per Section 9.1.1. Swabs will be resuspended in 1.5 mL tryptic soy broth (TSB) containing 15% (v/v) glycerol. Dilutions of culture medium will then be used to inoculate on mannitol salt agar plates with egg yolk for selective growth of *Staphylococcus* species and differentiation of coagulase-positive and coagulase-negative strains. Plates will be incubated for 24 hours in a 5% CO₂ incubator at 37° C. The plates will be evaluated for the presence of *S. aureus* colonies, which appear yellow with a surrounding clear zone.

9.1.3. 9.1.2. CFU Quantification of Live *Staphylococcus aureus*

Skin swabs will be collected from pre-measured areas of lesional and non-lesional skin per Section 9.1.1. Swabs will be suspended in 1.5 mL tryptic soy broth (TSB) containing 15% (v/v) glycerol and stored frozen at -80°C. Live CFUs of coagulase positive *S. aureus* will be determined by inoculation on a bacterial culture plate containing mannitol salt agar with egg yolk for selective growth of *Staphylococcus* spp. *S. aureus* will be conventionally distinguished from coagulase negative *Staphylococcus* according to mannitol metabolism and the egg yolk reaction, and coagulase positive and negative *Staphylococcus* will be quantified by manual counting of limiting dilutions of the stock solution.

9.1.4. Quantification of *Staphylococcus aureus*, *S. hominis*, *S. epidermidis*, and total *Staphylococcus* DNA by q PCR

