13.4.2 Primary Analysis of Primary Endpoint(s)/Outcome(s)

Aim: The change in *S. aureus* abundance after 7 days of AMT cream by using skin swabs to determine the quantity of *S. aureus* using culture and qPCR.

For each AD subject, the abundance of *S. aureus* will be calculated using CFU counts from baseline (day 28) to Day 35 after 7 days of AMT cream application or placebo application. Comparisons of *S. aureus* reduction will be made between AMT cream and placebo subjects using a two-tailed t-test for independent samples with type II error rate of 0.2 and type I error rate of 0.05. The sample size will include 18 subjects in the AMT cream arm and 9 subjects in the placebo arm. Comparisons of AMT cream versus placebo cream will be reported as means, standard deviations, medians, and minimum and maximum. An intention-to-treat analysis will be conducted that includes all subjects who had at least one follow-up visit after intervention. A per-protocol analysis will also be conducted that includes all subjects who were compliant with the full intervention regimen with no major protocol violations.

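### The primary test compares raw CFU differences although the effect of interest is a 10-fold reduction, which costs power unless counts vary little between subjects

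*Combined protocol and SAP*

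**What the plan says.** Section 13.7 fixes the scale of the endpoint: the change in S. aureus "will be measured as the absolute difference in number of colony-forming units at specified time points". Section 13.4.2 fixes the test: "Comparisons of *S. aureus* reduction will be made between AMT cream and placebo subjects using a two-tailed t-test for independent samples". Baseline enters only by subtraction.

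The effect of interest in section 13.7 is on another scale: "We observed that a log-base 10 reduction by 1 of the number of bacteria present on the forearms to be a clinically significant reduction". The power calculation then uses raw CFU/cm² from a five-patient pilot, measured 24 hours after treatment: 192.86 versus 19.186, with deviations 191.86 and 21.42. Of these inputs the section says "we used the median and median average deviation as measures of central tendency".

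The pilot description in section 1.4 reports a relative measure: S. aureus CFU "is shown as percent of baseline and different color symbols indicates data from each individual subject". Under section 9.1.3, staphylococci "will be quantified by manual counting of limiting dilutions of the stock solution". No section says how a zero or below-detection count enters the analysis.

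**The concern.** A 1-log10 reduction is a multiplicative effect, but the test statistic is additive. Two subjects with the same 10-fold response contribute 9 and 9,000 CFU/cm² if they start at 10 and 10,000. The arm mean, and even more its standard error, is then governed by the few most heavily colonised subjects.

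If counts are right-skewed, the planned test can miss a true 10-fold reduction that the same data would show on the log scale. There are only 9 placebo subjects and this is the sole primary analysis, so a working treatment could be reported as showing no effect. The medians and ranges promised in section 13.4.2 would expose the skew but would not correct the test. A change of scale after unblinding would look data-driven.

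**Working it through.** **1. The plan's own figure.** With the SD taken as the root mean of the two variances, √((191.86² + 21.42²)/2) = 136.51, the standardised difference is (192.86 − 19.186)/136.51 = 1.272. A two-sided 5% t-test with 2:1 allocation then needs 8 + 16 = 24 subjects (noncentral-t power 0.802; 0.850 at 9 + 18). The stated n = 24 is therefore reproduced and is not an arithmetic slip. The inputs, however, are medians and deviations of CFU levels. They are not the SD of a change, and they are not on the log scale.

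**2. What those inputs imply about shape.** A normal variable with mean 192.86 and SD 191.86 is negative with probability Φ(−192.86/191.86) = Φ(−1.005), about 16%. Counts cannot be negative, so the figures point to right skew. Under a lognormal model, the log10 SD depends on how 192.86 and 191.86 are read:

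- median and SD: 0.300
- mean and SD: √(ln(1 + (191.86/192.86)²))/ln 10 = 0.360
- median and median absolute deviation (half the distribution between 1.00 and 384.72): 1.587

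**3. Power.** Assumptions, because the documents supply neither quantity: log10 counts bivariate normal, baseline median 192.86, log10 SD s equal in both arms and at both times, baseline-to-Day-7 correlation ρ of 0.5 or 0.7, a 1-log10 fall on AMT only, 18 versus 9 subjects, 40,000 simulated trials per setting.

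| log10 SD | Raw-change t-test | log10 ANCOVA |
|---|---|---|
| 0.30 | 83–90% (Welch 78–88%) | 100% |
| 0.36 | 69–77% | 100% |
| 0.5 | 40–46% | 100% |
| 0.8 | 14–16% | 91–98% |
| 1.0 | 9% | 76–90% |
| 1.59 | 3% | 39–53% |

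**4. Where the gain comes from.** Power at ρ = 0.5 / 0.7 (20,000 trials per setting):

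| log10 SD | Raw change | Raw ANCOVA | log10 change | log10 ANCOVA |
|---|---|---|---|---|
| 0.5 | 41 / 46% | 95 / 96% | 99.7 / 100% | 99.9 / 100% |
| 0.75 | 17 / 20% | 64 / 71% | 88 / 98% | 94 / 99% |
| 1.0 | 9 / 9% | 36 / 41% | 66 / 86% | 76 / 90% |

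Subtracting a skewed raw baseline does much of the damage, and the raw scale does the rest. Once on the log scale, the covariate adds a smaller amount. The reason is that the SD of log10 change is s√(2(1 − ρ)), which is 1.00s at ρ = 0.5 and 0.77s at 0.7, while the ANCOVA residual SD is s√(1 − ρ²), which is 0.87s and 0.71s.

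**5. Influence and type I error.** The two largest of the 18 AMT subjects carry a median 28% of the summed absolute raw change at SD 0.30, 42% at 0.5, 60% at 0.8 and 86–87% at 1.59. Equal shares would be 2/18 = 11%. With no treatment effect, the raw test rejects in 4.4–4.7% of trials at SD 0.30–0.36, falling to 1.5–1.6% at 1.59. ANCOVA stays at 4.9–5.3%.

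**6. What n = 27 can support on the log scale.** By the noncentral t, an unadjusted t-test on log10 change has 80% power for a 1-log10 effect if the SD of that change is at most 0.84 (18 versus 9), or 0.79 (16 versus 8). At 18 versus 9 this corresponds to s = 0.84 at ρ = 0.5, or 0.84/0.775 = 1.08 at ρ = 0.7.

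**The case against.** The strongest reply is that the size of the harm is unknown. This is a single-centre phase 1 study, the raw test does not inflate false positives, and at a log10 SD of 0.30 it still has 83–90% power. That stands: the cost is power only, and on the most favourable reading of the pilot it is 10 to 17 points.

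The SD of 1.59 is fragile. It rests on one ratio, 191.86/192.86 = 0.995, from five patients; a ratio of 0.95 would give 1.05, and 0.90 would give 0.87. That also stands, so the 3% figure marks an extreme, and there even ANCOVA reaches only 39–53%. The conclusion does not need it, since the planned test is below 80% from a log10 SD of 0.36.

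The covariate could be called a preference, because change from baseline already uses baseline. In part this holds: on the log scale most of the gain is made without it. It still adds up to about 10 points at SD 1.0.

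The percent-of-baseline remark in section 1.4 follows the description of one figure panel, and the figure is not available, so it does not prove that the whole pilot was analysed on a relative scale. It is supporting evidence only.

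Finally, the share held by the two largest subjects describes skew and is not itself a measure of test failure. It is given here only as illustration.

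**Conclusion.** The concern holds. The endpoint and test in sections 13.7 and 13.4.2 are on a different scale from the effect the plan calls clinically significant, and the plan's own figures make symmetric raw counts implausible. Under lognormal counts, the planned test has less power than log10 ANCOVA at every setting tried. The loss is 10–17 points at a log10 SD of 0.30, 23–31 at 0.36, 54–60 at 0.5 and more than 70 at 0.8. More than half the power is lost only from an SD of about 0.5 upward.

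The sizes depend on a log-scale SD and a correlation that the documents do not give, and on the lognormal form, so no single figure can be stated. The direction is not in doubt under that model. Because this is the only primary analysis, it should be settled before unblinding.

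**What to change.** In sections 13.4.2 and 13.7:

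- Define the primary endpoint as log10 CFU/cm² of S. aureus by culture on lesional skin at the end of the 7-day application. Culture follows from the CFU counts in section 13.4.2, and lesional skin from the separate non-lesional secondary endpoint.
- Pre-specify the value used for zero or below-detection counts, with one sensitivity analysis using a different value.
- Test by ANCOVA with treatment arm and log10 Day 0 CFU/cm². Report the back-transformed fold-change ratio with its 95% confidence interval.
- Keep the raw means, SDs, medians and ranges as descriptive summaries.
- Restate the power of n = 27 on the log scale with an explicit SD, taken from the log-transformed pilot data if available, and compare it with the limits of 0.84 (18 versus 9) and 0.79 (16 versus 8).

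The cost is rewording, a redone power statement, one degree of freedom and one sensitivity analysis. No new data, visits or subjects are needed. The drawback is that the restated power may fall below 80%, which the sponsor would do better to know in advance.
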